## **2.6.4 Handling of missing values/censoring/discontinuations**

### **Handling of missing daytime asthma symptom scores and total daily SABA use**

The weekly mean will be calculated based on the non-missing post-baseline assessments as long as there are at least 4 days with non-missing data in a one-week period. Otherwise, the weekly mean will be set to missing. The multiple imputations will be carried out on the weekly mean data using J2R approach in a similar fashion as primary analysis described in [Section 2.5.4](#). The completed weekly mean data after imputation will be used in the model to calculate the mean of change from baseline over 12 weeks of treatment.

### **Handling of missing AQLQ+12 values**

The missing data of AQLQ+12 will be imputed using the same approach as primary analysis described in [Section 2.5.4](#).

## **2.7 Safety analyses**

All safety evaluation will be based on the safety analysis set.

### **2.7.1 Adverse events (AEs)**

All adverse events, including asthma exacerbations, coded with MedDRA using the most actual version at the time of database lock, will be listed. Unless otherwise specified, summaries will include treatment-emergent adverse events (TEAEs) only. AEs starting on or after the time of the first intake of study drug and not later than 7 days (30 days in the case of a serious AE) after the last intake of study drug will be classified as a TEAE. For those patients who enter the safety study (CQAW039A2315) directly after Visit 299, AEs (including serious AEs) starting after Visit 299 will not be considered as TEAEs in this study as they will be reported in CQAW039A2315.

As a general rule of censoring, patients who either completed the study or discontinue treatment prematurely and without the event of interest will be censored at the minimum out of the dates of last medication intake + 30 days, final visit date, and date of death. The number and percentage of patients who reported TEAEs will be summarized by primary system organ class (SOC), preferred term (PT), and treatment group for

- all adverse events (AEs)
- all AEs by maximum severity
- AEs suspected to be related to study drug
- AEs by standardized MedDRA query (SMQ) level
- serious AEs (SAEs)
- AEs leading to permanent study drug discontinuation
- AEs of special interest

Unless otherwise specified, primary system organ classes will be sorted alphabetically and, within each primary system organ class, the preferred terms will be sorted in descending order of frequency in the QAW039 150 mg once daily treatment group. If a patient reported more than one AE with the same preferred term, the AE will be counted only once. If a patient reported more than one AE within the same primary system organ class, the patient will be counted only once at the system organ class level.

In addition, the most frequent AEs will be presented by preferred term in descending order of frequency in the QAW039 150 mg once daily treatment group.

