The screening period allows for assessment of patient entry criteria and for patients to become familiar with spirometry measurement and daily eDiary entry prior to the collection of baseline values.

Patients experiencing an asthma exacerbation during the screening period must be designated as a screening failure. Patients who experience an asthma exacerbation during screening may be re-screened 4 weeks after complete recovery from the exacerbation.

Re-screening of patients is permitted once during the screening period.

Placebo run-in

The placebo run-in period allows for the determination of level of asthma control based on [REDACTED], FEV1 reversibility as determined by the central reader at the spirometry vendor, SABA use, and daytime asthma symptom scores for eligibility for randomization into the 12-week active treatment period. This period also allows for the collection of baseline data for all efficacy variables. During this period, patients will become familiar with administration of investigational treatment and patient's compliance with an Electronic Peak Flow/ eDiary device will be assessed.

Patients experiencing an asthma exacerbation during the placebo run-in period must be designated as a run-in failure.

Treatment period

During this period, oral QAW039 150 mg or matching placebo (1:1) will be administered once daily for 12 weeks added to SoC asthma therapy (as defined in inclusion criterion 4), with the last dose given at Week 12 and final assessment for the treatment period at Week 12. The 12-week treatment duration is considered sufficient to demonstrate an effect of QAW039 on the primary endpoint, pre-dose FEV1, in this Phase 3 study since QAW039 has previously demonstrated significant effects on pre-dose FEV1 in 12-week Phase 2 studies.

Follow-up period

The 4-week wash out period will monitor the safety and tolerability profile after the last dose of study drug.

The investigator must provide appropriate advice on the continued use of effective contraception for at least one week (at least 5 half-lives of QAW039) after the last dose of study drug and follow up with the subject as appropriate.

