9.5.1.3 AQLQ+12

The change from baseline in AQLQ+12 at week 12 will be analyzed using an ANCOVA model in a similar fashion as the primary efficacy variable. The baseline of AQLQ+12 is defined as the last assessment prior to the first dose of study drug. Missing data of AQLQ+12 overall score will be imputed a jump-to-reference approach as for the primary analysis.

9.5.1.4 **Summary statistics for the secondary variables**

Summaries of absolute values and change from baseline in the three secondary variables will be presented by visit and by treatment group. Figures will be produced to visually show the mean and the mean change from baseline by visit over study period for each treatment group.

9.5.2 **Safety variables**

All safety data will be summarized for the safety set.

9.5.2.1 **Adverse events**

Adverse events after informed consent including asthma exacerbations will be summarized and listed.

Adverse events starting on or after the time of the first intake of study drug will be classified as treatment-emergent adverse events. Any adverse events that started during the study after informed consent before the time of the first intake of study drug will be classified as a prior adverse events and not included in tabulations of treatment emergent adverse events.

The following treatment emergent adverse event summaries will be produced, overall by system organ class and preferred term, overall by system organ class, preferred term and maximum severity, suspected drug-related adverse events by system organ class and preferred term, serious adverse events by system organ class and preferred term, and adverse events leading to permanent discontinuation of study-drug by system organ class and preferred term.

The number and percentage of patients with the most frequent AEs will be summarized by treatment.

Selected adverse events of special interest may be summarized and analyzed as well.

9.5.2.2 **Vital signs**

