#### 4 Change to protocol specified analyses

- Section 9.2 in the study protocol states that the age of the patient will be calculated from the date of birth to date of Visit 1. However, since date of birth is not captured on the CRF page and age (in years) at the time of informed consent is entered into CRF, there is no need to re-calculate age.
- Shift tables relative to the normal reference ranges to summarize the on-treatment change from baseline to post-baseline for each laboratory parameter or ECG parameter or vital sign assessments will not be presented.
- Study protocol defines treatment emergent adverse events as those events starting on or after the time of the first intake of study drug and until the day after the last intake of study drug. However, in order to maintain consistency with the submission documents, for analysis purposes the following updated definitions are considered:  
AEs starting on or after the time of the first intake of study drug and not later than 7 days (30 days in the case of a serious AE) after the last intake of study drug will be classified as a TEAE.
- Added the responder analysis for AQLQ improvement
- Added more details to liver function tests including eDISH plot
- Added analysis for renal events and liver events according to project level alignment
- The following analyses, though pre-specified in the protocol, may not be critical for decision making purposes and hence will be reported outside of CSR:

█ [REDACTED]

- In protocol 9.4.4, supportive analysis for the primary endpoint based on other missing data imputation approaches: pattern mixture approach combining the jump to reference and missing at random approaches by distinguishing reasons for discontinuation of treatment and retrieved dropout imputation approach.
- In protocol Section 9.4.4, subgroup analyses for BMI, number of exacerbations in the previous year, ACQ tertiles, [REDACTED].
- Summaries on post-treatment discontinuation events to be produced for adverse events and serious adverse events by system organ class and preferred term.

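### SAP 2.7.1 narrows the protocol's open-ended definition of treatment-emergent adverse events, while SAP Section 4 misstates the protocol rule so that the change reads as an extension

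*SAP*

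**What the plan says.** Protocol 9.5.2.1 gives the definition: "Adverse events starting on or after the time of the first intake of study drug will be classified as treatment-emergent adverse events". It excludes events before first intake and sets no upper limit. Protocol 7.1 collects AEs from consent to the end of study visit.

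SAP 2.7.1 adds an upper limit, counting events that start "not later than 7 days (30 days in the case of a serious AE) after the last intake of study drug". It then sets the scope of the tables: "Unless otherwise specified, summaries will include treatment-emergent adverse events (TEAEs) only". All AEs, whatever their timing, are listed. For patients who roll directly into the safety study, events after Visit 299 are not treatment-emergent in this trial.

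SAP Section 4, which records departures from the protocol, says the protocol counts events "until the day after the last intake of study drug". It gives this reason for the change: "in order to maintain consistency with the submission documents, for analysis purposes the following updated definitions are considered". The last bullet of that section reads: "Summaries on post-treatment discontinuation events to be produced for adverse events and serious adverse events by system organ class and preferred term". It follows the sentence introducing analyses to be reported outside the CSR.

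On follow-up, Protocol 5.6.2 asks patients who stop drug to remain and complete all visits, and keeps AEs and serious AEs (SAEs) in the minimum data collected afterwards. The follow-up paragraph in Protocol Section 3 states: "The 4-week wash out period will monitor the safety and tolerability profile after the last dose of study drug".

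**The concern.** The current protocol and the current SAP define the same safety endpoint differently, and the section meant to disclose the difference describes the protocol side wrongly. A reader relying on Section 4 would conclude that more events are tabulated than the protocol planned. Against the protocol text, fewer are.

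Safety is a stated secondary objective, and the protocol makes a deliberate effort to collect AEs from patients who have stopped drug. Non-serious events starting more than 7 days after last intake, and serious events starting more than 30 days after, would not enter the AE summary tables of 2.7.1. What is at stake is the pre-specified between-arm AE comparison that continues past the point where drug is stopped. No efficacy conclusion is affected.

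**Working it through.** The plan gives no figure for this point, so the definitions are compared first and the off-drug time is sized afterwards.

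**Direction of the change**

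| Starting point | Ends for non-serious AEs | Ends for SAEs | SAP 2.7.1 relative to it |
|---|---|---|---|
| Protocol 9.5.2.1 as supplied | no limit | no limit | narrower: 7 and 30 days |
| Protocol as described in SAP Section 4 | last intake + 1 day | last intake + 1 day | longer by 7 − 1 = 6 and 30 − 1 = 29 days |

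The sign of the change depends on which description of the protocol is used. Only the first row matches the protocol.

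**Inputs for size**

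- 650 patients, 15% stopping drug early (Protocol 4 and 9.8): 650 × 0.15 = 97.5.
- Half of the stoppers have Week 12 FEV1 (Protocol 9.8), used here as a stand-in for AE follow-up to Week 12: 97.5 × 0.5 = 48.75.
- Treatment period to Day 84 (Protocol Table 6-1).
- Assumption, not in the documents: stopping times are uniform, so remaining follow-up U is uniform on 0 to 84 days with mean 42.

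**Early stoppers, off-drug time to Day 84 beyond a window of w days**

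E[(U − w)+] = (84 − w)² / (2 × 84)

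- Non-serious, w = 7: 77² / 168 = 35.3 days; 35.3 / 42 = 84%.
- Serious, w = 30: 54² / 168 = 17.4 days; 17.4 / 42 = 41%.
- Patient-days beyond the non-serious window: 48.75 × 35.3 ≈ 1,720.
- Planned treatment-period follow-up: 650 × 84 = 54,600 patient-days; 1,720 / 54,600 ≈ 3%. If every stopper is retained this doubles to about 3,440, or 6%.

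**Sensitivity to stop day (share of off-drug time to Day 84 beyond 7 days)**

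- Day 28: 49 / 56 = 88%
- Day 56: 21 / 28 = 75%
- Day 70: 7 / 14 = 50%

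**Completers who do not enter the safety study**

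In calendar time, 28 − 7 = 21 of 28 follow-up days (75%) lie beyond the non-serious window. The 30-day window covers all 28 days for SAEs. The 75% is not used as an effect size. In Table 6-1 the AE monitoring row appears to have no mark at Visit 301, whereas the SAE row has one, and Protocol 7.1 collects AEs to the end of study visit. How fully non-serious events are collected in those 21 days is unclear.

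**The case against.** The strongest reply is that a 7-day window is a sound main display. The protocol itself equates one week with at least five half-lives of the drug, and an on-treatment AE table alongside a treatment-policy efficacy estimand is not a contradiction, because the two answer different questions. That stands, and the 7/30-day tables should stay. Section 4 also states the new rule in full, gives a reason and calls it an update; it nowhere claims to widen anything. That stands too. The misleading effect comes from the wrong baseline, which may be left over from an earlier version or a template.

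Four stronger inferences are tempting, and the documents do not support them.

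- **That the only table of later events has been moved out of the CSR.** The bullet's position under the outside-CSR sentence is the natural reading, but bullet levels are flattened in the text. The visible part of SAP Section 5 does not repeat the item and allows analyses to be added back. Nor was anything clearly moved: that sentence describes its items as pre-specified, yet the protocol text contains no such summary.
- **That most off-drug non-serious AEs are lost.** The shares above are of time, not events, and the documents give no AE rates. Reading them as events needs an even rate. For early stoppers, most would fail if the rate in the first off-drug week were at least 35.3 / 6.7 ≈ 5.3 times the later rate.
- **That off-drug exacerbations reach no table.** They are monitored separately at every visit, and parts of the SAP are redacted, so this cannot be asserted.
- **That events disappear from the report.** All AEs and all deaths are listed.

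**Conclusion.** The conflict between Protocol 9.5.2.1 and SAP 2.7.1 is established from the texts alone, as is the error in Section 4's account of the protocol. The SAP window is narrower than the protocol's, and the section recording the change gives the opposite impression.

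The practical effect is modest and falls mainly on early stoppers who remain in the study: about 84% of their off-drug time to Day 84 is outside the non-serious window and about 41% outside the SAE window. This rests on uniform stopping times. The absolute amount, about 1,700 patient-days or roughly 3% of planned treatment-period follow-up, also rests on the plan's 15% stopping rate and on half of the stoppers being followed to Week 12. For completers the effect cannot be stated, because the protocol is unclear on non-serious AE collection at Visit 301.

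The affected events are absent from the summary tables specified in 2.7.1, not from the listings. This is a documentation error plus a low-cost improvement to the safety reporting. It does not show that the safety analysis is invalid.

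**What to change.** 1. Keep the 7/30-day treatment-emergent tables as the main display.
2. Correct SAP Section 4 to say that the protocol sets no end date, that the SAP window is narrower, and why it was chosen.
3. State that the CSR will contain one clearly labelled by-arm table, by system organ class and preferred term, of AEs and SAEs on the Protocol 9.5.2.1 definition (first dose to last study visit). Show separately the events that start after the treatment-emergent window. Continue to exclude events after Visit 299 for safety-study entrants.

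The cost is a wording change and one additional table from data already collected. The planned post-discontinuation summary covers part of that table but not all of it. The drawback is that off-drug events could be read as on-drug effects, so the separate labelling is essential.

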### **2.7.1.1 Adverse events of special interest / grouping of adverse events**

AEs of special interest definitions are found in the compound electronic Case Retrieval Strategy (eCRS). The classification reflects the current version of the dSPP and might be updated based on review of accumulating data. To identify AEs of special interest at the time of the final analysis, the latest version of the eCRS where Core safety topic risk (SP) = 'Yes' or Other Search risk (OS) = 'Yes' will be used.

The number and percentage of patients with treatment emergent AEs of special interest will be summarized by risk category, PT and treatment. In addition, summaries will be provided for

- Treatment emergent AEs of special interest by maximum severity
- Treatment emergent serious AEs of special interest
- Treatment emergent AEs of special interest that are suspected to be related to study drug

### **2.7.1.2 AE reporting for CT.gov and EudraCT**

For the legal requirements of clinicaltrials.gov, two required tables on TEAEs which are not SAEs with an incidence greater than a certain threshold based on the final database and on TESAEs and SAEs suspected to be related to study treatment will be provided by system organ class and PT on the safety set population.

If for a same patient, several consecutive AEs (irrespective of study treatment causality, seriousness and severity) occurred with the same SOC and PT:

- a single occurrence will be counted if there is  $\leq 1$  day gap between the end date of the preceding AE and the start date of the consecutive AE
- more than one occurrence will be counted if there is  $> 1$  day gap between the end date of the preceding AE and the start date of the consecutive AE

For occurrence, the presence of at least one SAE / SAE suspected to be related to study treatment / non SAE has to be checked in a block e.g., among AE's in a  $\leq 1$  day gap block, if at least one SAE is occurring, then one occurrence is calculated for that SAE.

The number of deaths resulting from SAEs suspected to be related to study treatment and SAEs irrespective of study treatment relationship will be provided by SOC and PT.

### **2.7.2 Deaths**

The number of deaths resulting from TEAEs will be summarized by SOC and PT. All the deaths in the clinical database including those occurring during screening will be listed.

### **2.7.3 Laboratory data**

Laboratory data consist of hematology, biochemistry and urinalysis measurements.

Laboratory data measured on or after first intake of study drug and until 7 days after last intake of study drug are regarded as on-treatment data. Laboratory data measured more than 7 days after last intake of study drug are regarded as post-treatment data and will not be summarized. All data will be included in the analyses regardless of rescue medication use. Results from local labs will be collected but not included in any analyses or summary tables because the reporting from local labs cannot be standardized. Results from central laboratories will be included in analyses and summary tables. Baseline laboratory data is defined in [Section 2.1.1.1](#). The following sub-sections will describe the method of summary.

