7.3 Liver safety monitoring

To ensure patient safety and enhance reliability in determining the hepatotoxic potential of an investigational drug, a standardized process for identification, monitoring and evaluation of liver events has to be followed.

The following two categories of abnormalities / adverse events have to be considered during the course of the study (irrespective of whether classified/reported as (S)AE):

- Liver laboratory triggers, which will require repeated assessments of the abnormal laboratory parameter
- Liver events, which will require close observation, follow-up monitoring and completion of the standard base liver CRF pages

Please refer to [Table 14-1 in Appendix 2](#) for complete definitions of liver laboratory triggers and liver events.

Every liver laboratory trigger or liver event as defined in [Table 14-1 of Appendix 2](#) should be followed up by the investigator or designated personal at the trial site as summarized below. Detailed information is outlined in [Table 14-2 in Appendix 2](#).

For the liver laboratory trigger:

- Repeating the liver function test (LFT) within the next week to confirm elevation.

These LFT repeats must be performed using the central laboratory if possible. If this is not possible, then the repeats can be performed at a local laboratory to monitor the safety of the patient. Repeats laboratory must then be performed at central laboratory as soon as possible. If a liver event is subsequently reported, any local LFTs previously conducted that are associated with this event must be reported on the Liver CRF pages.

Repeat laboratory tests must be entered on the appropriate unscheduled local laboratory CRF page.

- If the elevation is confirmed, close observation of the patient will be initiated, including consideration of treatment interruption if deemed appropriate.

For the liver events:

- Repeating the LFT to confirm elevation as appropriate
- Discontinuation of the investigational drug if appropriate
- Hospitalization of the patient if appropriate
- A causality assessment of the liver event via exclusion of alternative causes (e.g., disease, co-medications)
- An investigation of the liver event which needs to be followed until resolution.

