#### Liver function tests

To evaluate potential drug-induced liver injury, newly occurring or worsening abnormalities in liver function tests will be evaluated (see [Table 6-4-3](#) for a summary of the notable values).

When a criterion contains multiple laboratory parameters, the criterion will only be considered to be met when all conditions occur at the same time (i.e., in the same sample). A case where all criteria are met at a post-baseline time point but not met at baseline will be considered as newly occurring. A case will be considered as worsening if all the criteria are met at baseline and at least one component is worsening from baseline, irrespective of whether the other(s) are better.

The number and percentage of patients with newly occurring liver enzyme abnormalities any time post-baseline will be summarized. Listings of patients with notable liver function test lab values and liver events will be provided.

To evaluate drug induced serious hepatotoxicity eDish plots will be presented. The eDish plot will reflect the worst value of each of the parameters; they do not need to occur at the same visit.

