**Table 6-4-3 Notable liver function test values**

Criterion
ALT > 3 x ULN ALT > 5 x ULN ALT > 8 x ULN ALT > 10 x ULN ALT > 20 x ULN
ALT or AST > 3 x ULN ALT or AST > 5 x ULN ALT or AST > 8 x ULN ALT or AST > 10 x ULN ALT or AST > 20 x ULN
Total Bilirubin > 1 x ULN Total Bilirubin > 1.5 x ULN Total Bilirubin > 2 x ULN Total Bilirubin > 3 x ULN
ALP > 1.5 x ULN ALP > 2 x ULN ALP > 3 x ULN ALP > 5 x ULN
ALT or AST > 3 x ULN and Total Bilirubin > 1.5 x ULN ALT or AST > 3 x ULN and Total Bilirubin > 2 x ULN ALT or AST > 5 x ULN and Total Bilirubin > 2 x ULN ALT or AST > 8 x ULN and Total Bilirubin > 2 x ULN ALT or AST > 10 x ULN and Total Bilirubin > 2 x ULN ALT or AST > 20 x ULN and Total Bilirubin > 2 x ULN
ALP > 3 x ULN and Total Bilirubin > 2 x ULN ALP > 5 x ULN and Total Bilirubin > 2 x ULN
ALT or AST > 3 x ULN and Total Bilirubin > 2 x ULN and ALP ≤ 2 x ULN (Hy's law)
ALT or AST > 3 x ULN and (nausea or vomiting or fatigue or general malaise or abdominal pain or (rash and eosinophilia))*

ALT=alanine aminotransferase; AST=aspartate aminotransferase; ALP=alkaline phosphatase; ULN=upper limit of normal. \*Based on the signs/symptoms information as recorded on the liver events eCRF, not the adverse events eCRF.

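### SAP 2.7.3 keeps local liver-test results out of every analysis, so a case seen only in a local sample can be missing from the Table 6-4-3 counts and under-shown on the eDISH plot

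*SAP*

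**What the plan says.** **Which results are analysed.** SAP 2.7.3 says "Results from local labs will be collected but not included in any analyses or summary tables because the reporting from local labs cannot be standardized", and then "Results from central laboratories will be included in analyses and summary tables". It also treats laboratory values taken more than 7 days after the last dose as post-treatment and does not summarise them.

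**How liver tests are repeated.** Protocol 7.3 asks for repeats at the central laboratory where possible. It continues: "If this is not possible, then the repeats can be performed at a local laboratory to monitor the safety of the patient". A central sample must follow: "Repeats laboratory must then be performed at central laboratory as soon as possible". No time limit is attached. The local values are captured in two places. In general, "Repeat laboratory tests must be entered on the appropriate unscheduled local laboratory CRF page"; and if a liver event is later reported, "any local LFTs previously conducted that are associated with this event must be reported on the Liver CRF pages".

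**How liver injury is assessed.** SAP 2.7.3.3 (Liver function tests) counts patients meeting the Table 6-4-3 criteria, such as "ALT or AST > 3 x ULN and Total Bilirubin > 2 x ULN". Criteria with several components must be met in a single sample. For the eDISH plot the rule differs: "The eDish plot will reflect the worst value of each of the parameters; they do not need to occur at the same visit".

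**What the protocol planned.** Protocol 9.5.2.4 bases notable laboratory values on all data after baseline, with unscheduled and early-discontinuation visits included, and states no exclusion of local results. SAP 2.7.3.3 repeats that scope. SAP Section 4, which lists departures from the protocol's analyses, does not mention local laboratories.

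**The concern.** The protocol deliberately collects local liver tests, and the SAP then bars them from the outputs it uses to look for drug-induced liver injury. The bar rests on one reason, lack of standardisation, and is applied to all parameters alike. For the Table 6-4-3 thresholds that reason is weak, because a value divided by the upper limit of normal (ULN) of the laboratory that measured it is already on the scale of the criterion.

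At stake is whether the Hy's law row, the other Table 6-4-3 counts and the eDISH plot show every case that the trial's own records contain. Such events are rare, so one patient can decide whether a row reads zero. The narrowing is also undeclared: a reader comparing the protocol with SAP Section 4 would not learn of it.

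**Working it through.** The plan gives no figure on this point, so there is nothing to reproduce. The check compares the passages and adds one illustration of scale.

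**1. Does the stated reason apply?** Every laboratory threshold in Table 6-4-3 (ALT, AST, total bilirubin, ALP) is a ULN multiple. The final row adds symptoms, which the table's footnote takes from the liver events eCRF, so the SAP already uses liver CRF data for this table. By contrast, several criteria in Table 6-4-2 are in absolute units, where the standardisation argument has more force. The reason therefore supports a general exclusion better than it supports one for the liver criteria.

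**2. When is a central value available?** Table 6-1 places central chemistry at Visits 1, 201, TD and 299. After baseline that means the treatment discontinuation visit and Week 12; there is none at Weeks 2, 4 or 8. An event between visits depends on an unscheduled sample, on the central repeat that Protocol 7.3 requires after a local one, or on the TD sample.

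**3. What happens to a patient whose qualifying values are in a local sample?** It depends on the central samples after onset:

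| Central sample after onset | Table 6-4-3 combined row | eDISH plot |
|---|---|---|
| Within the 7-day window, combination met | Counted | Shown, possibly below peak |
| Within the window, components raised but not all in one sample | Not counted | Shown at the worst central values |
| Within the window, values already below the thresholds | Not counted | Shown low |
| None within the window | Not counted | Only earlier central values, or absent |

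The last three rows are the gap. The single-sample rule means that a later, falling central sample does not restore a combination met locally. The window can add to this. Table 14-2 stops study drug immediately for a potential Hy's law case or jaundice, so the 7 days start then, while the central repeat has no stated limit. One qualification: the liver paragraph of SAP 2.7.3.3 refers to abnormalities at any time after baseline, but does not say that it sets the 2.7.3 window aside.

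**4. Scale.** Input: 325 patients per arm (Protocol 9.8, SAP Section 3). Assumption: exactly one Hy's law case on QAW039, met only in a local sample.

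- With the local value: 1/325 = 0.31%; exact (Clopper-Pearson) two-sided 95% upper limit 1.70%.
- Without it: 0/325 = 0%; upper limit 1 − 0.025^(1/325) = 1.13%.

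This shows what one case is worth in the table. It does not estimate how often a case would be lost: the documents give no frequency of local testing, so that cannot be computed.

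**The case against.** The case for the plan is substantial. Local testing is a fallback: Protocol 7.3 puts the central laboratory first and requires a central repeat after any local one, and Protocol 6.5.4 makes the central laboratory the default for chemistry. Where a local repeat follows a central trigger value, that central value is already analysed. A patient who stops study drug is asked back promptly for the TD visit (Protocol 5.6.2), where central chemistry is taken. Since the eDISH plot takes the worst value of each parameter across visits, any raised central sample within the window still plots the patient. Finally, no passage says that local reference ranges are recorded, so conversion to ULN multiples may not always be possible.

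All of this stands, and it limits the point. Three stronger readings are tempting and are not supported:

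- *That acute liver values are usually local.* Table 14-2 asks for some repeats within 48 hours and for hospitalisation with jaundice. That makes local testing plausible, but says nothing about its frequency.
- *That no central liver test falls between Day 1 and Week 12.* The TD visit is an exception, and it applies to the patients who stop drug for a liver event.
- *That a Hy's law case would disappear from the report.* A potential Hy's law case is a liver event under Table 14-1 and requires the liver CRF. SAP 2.7.6 summarises treatment-emergent liver events by arm and lists all of them, and SAP 2.7.3.3 lists patients with liver events. Appendix 4 also counts liver events as potential idiosyncratic reactions, which Protocol 7.7 sends to the DMC.

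What remains is that none of these safeguards corrects the Table 6-4-3 counts or restores the peak on the eDISH plot.

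**Conclusion.** The point holds as a gap in the laboratory-based liver outputs. A patient whose peak or combined criterion is seen only locally can be uncounted in Table 6-4-3, including the Hy's law row, and be under-shown or absent on the eDISH plot. The same report should still show that patient as a liver event, so the two sets of outputs could disagree without explanation.

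The conclusion rests on three conditions: a local test was used, no central sample inside the analysis window met the criterion, and the 2.7.3 window governs the liver table. Only the first two are needed where a central sample was taken in time but had already fallen. The size in practice is unknown; the single-case illustration is the most that the documents allow. The omission from SAP Section 4 does not depend on any of these conditions. This is a worthwhile and inexpensive correction to reporting, not a threat to the trial's conclusions on efficacy.

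**What to change.** In SAP 2.7.3, keep the exclusion of local results for by-visit means and the other laboratory summaries, and add an exception for liver tests. In SAP 2.7.3.3, where the local ULN is recorded, include local ALT, AST, total bilirubin and ALP as multiples of the reporting laboratory's ULN, flagged as local, in:

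- the Table 6-4-3 counts, shown with and without local values and with the single-sample rule applied unchanged to each local sample;
- the eDISH plot, with a distinct symbol for local values;
- the liver listings. SAP 2.7.3 does not mention listings and Protocol 9.5.2.4 lists all laboratory data, so this part only makes the intention explicit.

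In SAP Section 4, state the local-laboratory exclusion that remains as a change from Protocol 9.5.2.4.

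The cost is SAP wording and minor programming on values already collected. The downside is some between-laboratory variation, which the flag and the paired counts make visible. Local values without a recorded ULN can only be listed, so the sponsor should first confirm whether the CRF captures local reference ranges.
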